9 STUDY COMPLETION AND REMUNERATION

At the last scheduled protocol visit a study completion form (ADMIN 2) will be completed, which requires the signatures of both the participant and the investigator. The participants will also be provided with a letter of appreciation (ADMIN 1).

Once their involvement in the study is complete, participants will be informed about receiving feedback following study completion in the Letter of Appreciation (ADMIN 1).

Participant remuneration will be \$95 for completing the study. Participants will be asked to sign a Study remuneration form (ADMIN 4), acknowledging that they have received remuneration for their involvement in the study.

10 STATISTICAL ANALYSIS AND DATA MANAGEMENT

10.1 STATISTICAL ANALYSIS

All data will be analyzed by CORE at the University of Waterloo. Unmasked data analysis will be conducted using Statistica 13 or later. Descriptive statistics will be provided on information regarding baseline variables (age, sex, refractive error distribution, etc.). For data collected on each eye individually (e.g. biomicroscopy), results of the right eye will be reported unless a difference between right eye and left eye is found. Table 3 lists the primary and other outcome variables and anticipated statistical procedures. All data will be tested for normality of distribution using Shapiro-Wilk tests. Statistical significance will be set at 5%. Superiority testing for the primary outcome variable (i.e. VAS ratings for CL-related discomfort and dryness at 12–weeks vs baseline) will be performed, using a superiority margin of 10 units on the 100-point scale. Additional statistical testing may be applied as required.

Table 4: Statistical procedures

Variable	Analysis	Statistical test
CLDEQ-8 score,	Descriptive statistics	Mean, Standard Deviation
 VAS ratings, Pre-lens non-invasive tear breakup time (PLNITBUT), bulbar and limbal redness, tear inflammatory markers; 	Effect of time on the outcome variables (Comparison between visits)	RMANOVA/MANOVA Mauchly's test of sphericity Huynh-Feldt p values Tukey HSD post hocs Paired t-test
Safety measures (biomicroscopy, visual acuity.)	Descriptive statistics Effect of safety and exploratory variables over time	Mean, Standard Deviation RMANOVA/MANOVA Mauchly's test of sphericity Huynh-Feldt p values Tukey HSD post hocs Paired t-test

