4.4.2 BASELINE & DISPENSE (VISIT 2; DAY 0)

Participants will attend the baseline & dispense visit after having worn a new pair of their habitual lenses for at least 6 hours prior to visit start. No habitual eye drop use is permitted on the day of this study visit. Participants are asked to bring their habitual spectacles to the visit, to be worn prior to leaving the visit after Xiidra study drop application. Baseline measurements and evaluations will be performed prior to dispense of the Xiidra study drops.

The following evaluations/procedures will be performed, in the order outlined below:

- Changes in medical history and medications;
- Comfortable lens wear and total lens wear time;
- Questionnaires
 - CLDEQ8 questionnaire;
- Subjective ratings of ocular symptoms
 - Visual analog scales, including determination of Eye Dryness Score^{4,5}
- Monocular high contrast visual acuity with habitual CL;
- Non-invasive tear break-up time over habitual CL (PLNITBUT);
- Lens performance (fit & wettability) assessment (with habitual CL);
- Bulbar & limbal redness (with habitual CLs on eye; Efron scale & K5M);
- Lens removal;
- Tear film collection;

- Slit lamp biomicroscopy using fluorescein (Safety);
- First application of Xiidra study drops
- Post-drop: Subjective ratings of symptoms and tolerability
- Monocular high contrast visual acuity with habitual spectacles or habitual CL;
- Dispense of Xiidra drops, including review of drop application process and frequency. Participants are also being reminded to not use the drops with CLs on eye;
- Dispense of habitual study lenses and care solution (if applicable) to last until the next study visit; one additional pair will be included to replace the new pair worn when attending this visit.

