4.4.7 STUDY EXIT

The Study Exit form must be completed when a participant exits the study. This will occur either at study completion or if the participant is discontinued from the study at another time. A Study Exit form must be completed for all participants who have been allocated a study ID number. Post-study follow-up visits will be scheduled if the investigator determines this is necessary and the exit form will be signed after the last follow-up visit.

At the Study Exit Visit the following details are required:

- Visual acuity with habitual lenses, spectacles or refraction (logMAR);
 - If the VA at the Exit Visit is two or more lines worse than at baseline, the investigator will be required to provide an explanation and complete an adverse event form.

• Post-study follow-up requirement (Y/N): If yes, the reason and date of the follow-up visit must also be recorded.

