4.5.8 SLIT LAMP BIOMICROSCOPY

The participant will be seated behind a slit lamp and the following will be assessed:

Cornea:

Any current or past corneal observations (such as infiltrates, old scars, etc) will be documented at each visit.

Corneal and conjunctival staining

A sodium fluorescein strip, wetted with a few drops of saline, will be applied to the superior bulbar conjunctiva of both eyes. Staining will be graded using the Efron scale (0 to 4, 0 = normal) while viewing with cobalt blue light through a Wratten no. 12 barrier filter.

Palpebral conjunctival hyperemia and roughness

The redness and roughness of the upper and lower eyelids (tarsal plate zone 2) will be assessed using the EFRON Grading scale (0 to 4, 0 = normal/ uniform satin appearance).

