7 ADVERSE EVENTS

See CORE SOP012_v02 for a description of all adverse events, including management and reporting.

An 'adverse event' (AE) refers to any untoward medical occurrence in a subject administered an investigational product or subjected to an investigational study procedure. Any observations taking place prior to determining that a subject meets all inclusion / exclusion criteria for the study and which are not related to the performed study procedures are not considered an AE. An AE can therefore be any unfavourable and unintended sign, symptom, or disease temporarily associated with the investigational product / study procedure, whether there is a causal relationship or not.

A number of conditions may result in temporary suspension until resolution. These include corneal infiltrates, corneal staining, limbal injection, bulbar injection or tarsal conjunctival abnormalities.

To maintain pharmaco-vigilance, information regarding all AEs, SAEs and pregnancies will be collected during the trial and reported according to local regulations. Clinical information about any adverse event will be collected on the standard CORE adverse events clinical report form. Serious adverse events will be reported within 24 hours to the Office of Research Ethics using their Adverse Event Report Form 106.

CORE will also inform the funding agency, Novartis, of all serious adverse events within 24 hours of becoming aware. Unusual failures in efficacy, reports of drug exposure during pregnancy and reports of study drug misuse or abuse, including initial and follow up reports, arising from the study in subjects exposed to the study drug will be reported to Novartis, as soon as it becomes available, but in any event within fifteen (15) calendar days of becoming aware of such information.

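### Section 10.1 shows the left eye only if an undefined right-left difference is found; judged for the group, a few left-only safety findings could go untabulated

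*Combined protocol and SAP*

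**What the plan says.** Section 10.1 sets one rule for all data recorded on each eye, with biomicroscopy as its example: "results of the right eye will be reported unless a difference between right eye and left eye is found". It gives no criterion for finding a difference and does not say what is reported once one is found. The 5% significance level appears in the same section but is not tied to this check. The tests in Table 4 concern change over time; none compares right with left.

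Table 4 names biomicroscopy and visual acuity as the safety measures and gives mean and standard deviation as their only descriptive summaries.

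Left-eye safety data are collected. For staining, section 4.5.8 says fluorescein "will be applied to the superior bulbar conjunctiva of both eyes", with grading on a 0 to 4 scale. The visit schedules list "Monocular high contrast visual acuity with habitual CL", so acuity is recorded per eye.

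Several safeguards are not limited to one eye:
- Section 7 says that "information regarding all AEs, SAEs and pregnancies will be collected during the trial", and lists slit-lamp findings that may lead to temporary suspension.
- Section 4.4.7 requires an explanation and an adverse event form "If the VA at the Exit Visit is two or more lines worse than at baseline".
- Section 4.5.8 has corneal observations documented at every visit.
- Section 8 has all discontinuations, with reasons, in the final report.

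**The concern.** Whether the left eye appears in the safety tables depends on the data, through a criterion that is not written down. Two analysts could produce different safety tables from the same records. The analysis is unmasked and the study open-label, so the choice would be made with results in view.

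Under a group-level check, findings in the left eye of a few participants would usually be too few to count as a difference, and the tables would show the right eye alone. The findings at stake are left-eye biomicroscopy grades and acuity changes that are not recorded as adverse events. Section 4.3.2.2 says one container can be used to dose both eyes, so the left eye is as relevant to safety as the right.

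**Working it through.** The plan gives no figure for this rule, so there is nothing to reproduce. The calculations show what one reading would do.

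**Inputs.** From the plan: n = 40 completers (section 4.2.2, with up to 55 dispensed) and the 5% level (section 10.1). Assumed: the check is a two-sided group-level test of one variable at one visit, and k participants have a left-only finding of one grade.

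**Per-participant reading.** Any participant whose eyes differ triggers reporting. Nothing is missed, whatever k is.

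**Group-level reading, all other right-left differences zero.** The differences are k ones and n − k zeros, so the paired t statistic is t = √[(n − 1)k / (n − k)] on n − 1 degrees of freedom. The exact sign test gives p = 2 × 0.5^k.

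| k of 40 | t | Paired t, p | Sign test, p |
|---|---|---|---|
| 1 | 1.00 | 0.32 | 1.00 |
| 2 | 1.43 | 0.16 | 0.50 |
| 3 | √(39 × 3/37) = 1.78 | 0.083 | 0.25 |
| 4 | √(39 × 4/36) = 2.08 | 0.044 | 0.125 |
| 5 | 2.36 | 0.023 | 0.0625 |
| 6 | 2.62 | 0.012 | 0.031 |

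Up to 3 participants (t-test) or 5 (sign test) would go unflagged. With n = 55 the t-test cut-off is the same: k = 3 gives p = 0.083 and k = 4 gives p = 0.044.

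**With ordinary right-left variation.** In simulation with normal right-left differences (SDs assumed), the paired t-test flags a difference this often:

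| k of 40 | SD 0.25 grade | SD 0.5 grade |
|---|---|---|
| 3 | 16% | 10% |
| 5 | 42% | 21% |

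**Acuity.** A left-only loss of 0.2 logMAR in 3 of 40 moves the left-eye mean by 3 × 0.2/40 = 0.015 logMAR. With an assumed difference SD of 0.05 or 0.10, it is flagged in about 16% or 10% of runs.

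**Table 4's summary, if the left eye is shown.** With k eyes at grade 1 and the rest at 0, the mean is k/n and the SD is √[k(n − k) / (n(n − 1))].
- k = 3: mean 0.075, SD √(111/1560) = 0.27. A count reads 3/40 (7.5%).
- k = 5: mean 0.125, SD √(175/1560) = 0.34. A count reads 5/40 (12.5%).

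Showing the left eye is therefore not enough unless counts are added.

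**The case against.** The strongest reply is that the loss depends on how the rule is read. The plan says a difference, not a significant or group difference, and lists no right-left test. On a per-participant reading nothing is lost. This stands, and it is why the loss is stated as conditional. But the plan does not adopt that reading, nor say how such a participant would then enter a table of group means.

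A second reply is that little may fall outside adverse event reporting. Section 7 sets no grade threshold and defines an adverse event broadly enough to include an unwanted sign, whether or not the drop caused it. A new left-eye staining grade could qualify, and several slit-lamp findings may lead to suspension. This also stands. How the line is drawn is left to a site procedure (CORE SOP012_v02) that is cited but not included, so the size of the remainder is unknown. The safeguards are still not tabulation: the acuity trigger is stated only for exit, and no section says that the documented corneal observations will be tabulated.

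A third reply is that nothing suggests left-sided effects, so the right eye gives a fair per-eye rate. That is correct for the rate. It does not give the number of participants affected. With five right-only and five left-only findings, the mean right-left difference is zero and the rule is not triggered. The right-eye table then shows 5 affected participants where there are 10.

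A reader might infer that left-eye safety data are not collected, that left-eye adverse events would be lost, or that the safety results would be biased. The documents do not support any of these: both eyes are examined, adverse event collection is not limited by eye, and the rule governs reporting only.

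**Conclusion.** The point holds as a minor reporting gap. The plan establishes a data-dependent rule with no stated level, test or visit. The possible loss arises only if the rule is applied to the group. On the assumed two-sided 5% test at one visit, left-only one-grade findings in up to 3 of 40 participants (paired t) or 5 of 40 (sign test) would go unflagged when there is no other right-left variation. The flagging rates with such variation rest on assumed SDs.

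What could be missing is limited to left-eye grades and acuity changes not recorded as adverse events, and the documents do not show how many these would be. The primary outcome is unaffected, because section 4.5.2 has the VAS rated for both eyes together. Nothing is lost from the study records, so the gap can be closed before analysis.

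**What to change.** In section 10.1, replace the conditional rule for safety measures with:

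> Biomicroscopy and visual acuity will be tabulated for the right eye and the left eye separately at each visit, with the number of eyes at each grade (or acuity-change category) in addition to mean and SD; the number of participants with a worsening from baseline in at least one eye will also be given, each participant counted once.

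Add the counts to the safety row of Table 4. State the acuity-change categories and what counts as a worsening, and use whole-grade bands if grades are recorded in decimals.

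For other outcomes measured in both eyes, fix one eye rule in advance, such as the participant mean of both eyes. This concerns redness and pre-lens break-up time, where sections 4.5.4 and 4.5.6 should state which eyes are measured, and the tear markers, since section 4.5.7 collects tears from each eye.

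The cost is a few sentences and slightly longer safety tables. The safety change needs no new data, visits or participants.

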4.2 STUDY POPULATION

4.2.1 SAMPLE SIZE CALCULATION

This is a pilot study. As no data on contact lens wearers using Xiidra are available yet, a number of 40 symptomatic wearers has been estimated as sufficiently large to detect differences in comfort ratings at 12 weeks compared to baseline. The data collected in this pilot study may be used to calculate sample size for future studies.

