4.2.2 NUMBER OF PARTICIPANTS

Participants will be recruited using CORE records and advertising approved by the UW Office of Research Ethics. Up to 55 eligible participants may be dispensed with study products, with a target of 40 participants completing the study. Informed consent will be obtained for all participants prior to their enrolment in the study (Appendix 1).

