4.5.2 QUESTIONNAIRES AND SUBJECTIVE RATINGS

Questionnaires

At screening; participants will be asked to assess the intensity and frequency of their CL associated dryness symptoms late in the day. Participant will be categorized as dry eye based on Young's categorization⁷ (dark grey areas in Table 3 below):

Table 3: Young's categorization for contact lens dry eye score

Categorization grid for the Contact Lens Dry Eye score.

		Never	Frequency of dryness				
			Rarely	Sometimes	Frequently	Constantly	
	Never have it – 0	No	No	No	No	No	
	Not at all intense - 1	No	No	No	No	No	
Intensity of late-day dryness	2	No	No	Marginal	Marginal	Marginal	
	3	No	No	Yes	Yes	Yes	
	4	No	No	Yes	Yes	Yes	
	Very intense – 5	No	No	Yes	Yes	Yes	

Note: Score derives from the combination of responses to frequency and intensity of dryness late in the day. Dark grey, Dry; light grey, Marginal; white, Not Dry.

Participants will complete the CLDEQ8 at every visit, reporting their experience with their habitual contact lenses in the last 2 weeks before a study visit.

Subjective ratings

Participants will be asked to complete subjective ratings of their ocular symptoms at each study visit.

Participants will be asked to rate their ocular symptoms (OU) on a 7-item visual analog scale (VAS;

Appendix 2) for a 0 (none) to 100 (worst) range; the VAS includes the following items: burning/stinging; itching; foreign body sensation; eye discomfort; eye dryness; photophobia; pain. At the screening visit, the eye dryness VAS rating needs to be >40 for a participant to be eligible.

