4.5.4 NON-INVASIVE BREAK-UP TIME (PRE-LENS)

The participant will be seated in front of a device that will project rings of light (Placido discs) onto the tear film. The participant will be asked to keep their eyes open for as long as they can and the time until the rings first begin to distort or break will be recorded. Three measurements will be taken to obtain an average value.

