4.5.6 OCULAR REDNESS (WITH CL)

Ocular redness will be assessed for the bulbar and limbal conjunctiva, with CLs still on the eye. Assessments will include subjective grading using the EFRON Grading scale (0 to 4, 0 = normal; 0.1 increments) as well as objective measurements using the Keratograph K5M (0 to 4, 0.1 increments). To avoid potential investigator bias, subjective grades using the Efron scale will always be obtained prior to the K5M measurements.

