4.5.7 TEAR FILM COLLECTION

Tears will be collected by holding a small, disposable, sterile glass tube near the participant's lower lid without touching the surface of the eye. During the procedure, participants will be allowed to blink normally. Tears will be collected from each eye until at least 5ul of basal tears have been collected, or after a maximum of 5 minutes collection time, whichever occurs first. All tear samples will be individually labeled with a study code (no participant names will be on these labels) and frozen until further processing. Tear samples will be analyzed for lipid and anti-inflammatory mediator concentration. Any remaining or resulting chemical combinations will be disposed of using standard laboratory procedures as outlined by the UW Safety Office.

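### Outcomes measured per eye are reported from the right eye, with an undefined exception if the eyes differ; a pre-specified two-eye mean would use the left-eye data and remove the exception

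*Combined protocol and SAP*

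**What the plan says.** Section 10.1 sets one rule for everything measured eye by eye. It opens "For data collected on each eye individually (e.g. biomicroscopy" and continues that "results of the right eye will be reported unless a difference between right eye and left eye is found". Biomicroscopy is given only as an example, so the per-eye efficacy outcomes in section 2 (tear inflammatory markers, ocular redness, PLNITBUT) are not exempt. The section names no test, level or visit for finding a difference, and does not say whether the left eye, both eyes or a mean is reported when one is found. Table 4 lists repeated-measures ANOVA/MANOVA and paired t-tests over time. It includes no two-eye summary and no model with eye within participant.

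The measurement sections differ in how clearly they cover both eyes:
- Tears (4.5.7): "Tears will be collected from each eye until at least 5ul of basal tears have been collected", or until a 5-minute limit is reached. Samples are labelled individually. Whether the two eyes are assayed separately or pooled is not stated.
- Redness (4.5.6): "Ocular redness will be assessed for the bulbar and limbal conjunctiva, with CLs still on the eye". The number of eyes is not stated.
- PLNITBUT (4.5.4): "Three measurements will be taken to obtain an average value". The number of eyes is not stated.

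The primary outcome is per person: "Participants will be asked to rate their ocular symptoms (OU) on a 7-item visual analog scale" (4.5.2).

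**The concern.** Participants wear lenses in both eyes (inclusion criterion 4), and 4.3.2.2 notes that one container can dose both. Both eyes then carry information about the same within-person change. Two things follow from the rule.

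First, the default estimate for a per-eye outcome ignores the left-eye value, although the rule can be applied only if that value exists. The change estimate is less precise than the data would allow. This matters somewhat in a study aiming for 40 completers whose data may be used to plan later studies (4.2.1).

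Second, because the exception is undefined, two analysts could follow section 10.1 faithfully and report different things. What is reported depends on the observed data, in an analysis that section 10.1 describes as unmasked.

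The plan also does not say what happens when one eye's value is missing at a visit.

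**Working it through.** **Plan's own figure.** There is none to reproduce here. No precision or power is stated for the per-eye outcomes. The target size rests on judgement and concerns comfort only: "a number of 40 symptomatic wearers has been estimated as sufficiently large to detect differences in comfort ratings at 12 weeks compared to baseline". I use n = 40 from there and from 4.2.2 ("Up to 55 eligible participants may be dispensed with study products, with a target of 40 participants completing the study").

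**Inputs.**
- n = 40 completers (4.2.1, 4.2.2).
- Significance level 5% (10.1), taken as two-sided; the plan does not say.
- rho, the between-eye correlation of the change from baseline: not in the documents. Assumed, with 0.3 to 0.95 shown.
- Equal variance of the change in the two eyes: assumed.

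**Formula.** Let D_R and D_L be a participant's right-eye and left-eye changes, each with variance s².

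Var[(D_R + D_L)/2] = (s² + s² + 2·rho·s²)/4 = s²(1 + rho)/2

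The standard error of the two-eye mean, relative to one eye, is therefore sqrt((1 + rho)/2). The number of participants a one-eye analysis would need for the same precision is 40 / ((1 + rho)/2).

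Example at rho = 0.5: (1 + 0.5)/2 = 0.75; sqrt(0.75) = 0.866; 40/0.75 = 53.3.

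| rho (assumed) | SE ratio | Interval narrower by | One-eye n for same precision | Power if the one-eye analysis has 80% |
|---|---|---|---|---|
| 0.3 | 0.806 | 19.4% | 61.5 | 93.5% |
| 0.5 | 0.866 | 13.4% | 53.3 | 89.9% |
| 0.7 | 0.922 | 7.8% | 47.1 | 86.0% |
| 0.8 | 0.949 | 5.1% | 44.4 | 84.0% |
| 0.9 | 0.975 | 2.5% | 42.1 | 82.0% |
| 0.95 | 0.987 | 1.3% | 41.0 | 81.0% |

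The power column uses the paired t-test with n = 40. It takes the standardised change that gives 80% power on one eye (0.454 SD) and divides it by the SE ratio. It is an illustration only, because the plan states no power for these outcomes. At rho = 1 there is no gain.

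**The exception.** No arithmetic applies. To attach an error rate to it one would need the test, its level, the visits at which it is applied and what is reported afterwards, and section 10.1 gives none of these.

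**The case against.** The case for leaving the rule alone is substantial. A fixed right-eye analysis is valid and unbiased, and it avoids the real error of counting two eyes of one person as independent. Averaging is thus an efficiency choice, not the repair of a mistake. The gain depends wholly on an unknown rho and nearly vanishes at 0.9 or above. The exception can fairly be read as a disclosure rule (show both eyes when they differ), and a mean alone would hide such asymmetry. Measurement of both eyes is explicit only for tears. Redness and PLNITBUT rest on inference from bilateral lens wear and the per-eye rule, and tears might be pooled before assay. The primary VAS is untouched, and this is an uncontrolled pilot.

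All of this limits the size and reach of the point, and none of it removes it. With similar variances, the two-eye mean is more precise for any rho below 1 and still counts each participant once. Asymmetry stays visible if the eyes are also tabulated separately. Pooling is a caveat only, since a rule comparing right with left presupposes a result from each eye.

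A reader might infer three stronger things that the documents do not support:
- That chance decides which eye is presented. Section 10.1 names no test and does not say that the left eye replaces the right.
- That a number of false right-left differences can be predicted. Any such count needs a testing scheme that the plan does not contain.
- That a right-eye tear sample cut short at 5 minutes leaves no usable value for the visit. Section 4.5.7 gives a rule for stopping collection, not a minimum assay volume.

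**Conclusion.** The point holds in a limited form. Section 10.1 defaults to the right eye for outcomes that it presupposes are available from both, and attaches an exception whose trigger and consequence are both undefined. The lack of definition holds whatever rho is.

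The loss of precision depends on rho. Replacing the right eye by the two-eye mean shortens confidence intervals by about 13% at rho 0.5, 5% at 0.8 and 2.5% at 0.9. These figures assume similar variances in the two eyes and that both eyes are measured and assayed. Only the non-primary per-eye outcomes are affected. The primary VAS comparison and the target of 40 are not, and right-eye results produced under the default would not be biased.

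**What to change.** In section 10.1, for tear markers, redness and PLNITBUT, where both eyes are measured:
- analyse the mean of the two eyes per participant and visit, on the log scale for the markers;
- if only one eye has a value, use that eye and flag it;
- delete the right-left exception for these outcomes;
- tabulate right and left eyes separately, as description only, so that asymmetry stays visible.

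It would help to state in 4.5.4 and 4.5.6 that both eyes are measured, if that is the intention, and in 4.5.7 that the eyes are assayed separately.

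The cost is a change to the SAP text and slightly more analysis work. Assay work increases only if the intention was to pool the tears or to assay one eye.

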2 OBJECTIVES

The primary objective is to investigate whether comfort and dryness in symptomatic contact lens (CL) wearers improve after using Xiidra (lifitegrast 5.0% ophthalmic solution) for 12 weeks. In addition, this study will also evaluate whether the quantity of tear film inflammatory markers changes after use of Xiidra for 12 weeks.

The primary outcome variables for this study are subjective ratings of 'CL-related discomfort and dryness', as part of the visual analog scale (VAS) for symptom assessment, at 12 weeks compared to baseline.

Other outcome variables for this study include:

- Subjective ratings of CL-related discomfort and dryness, as part of the visual analog scale (VAS) for symptom assessment, at two and six weeks compared to baseline;
- CLDEQ-8 score at two, six and 12 weeks compared to baseline;
- Quantity of tear film inflammatory markers after 6 hours of CL wear at two, six and 12 weeks compared to baseline
 - o Inflammatory markers for 10 cytokines will be evaluated using the MSD (MesoScale Discovery) platform. The Proinflammatory Panel 1 (human) Kit will be used; it provides assay-specific components for the quantitative determination of IFN-γ, IL-1β, IL-2, IL-4, IL-6, IL-8, IL-10, IL-12p70, IL-13, and TNF-α.
- Ocular redness at two, six and 12 weeks compared to baseline;
- Non-invasive tear break-up time (pre-lens; PLNITBUT) at two, six and 12 weeks compared to baseline.

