3 HYPOTHESIS

The primary hypothesis is that symptomatic CL wearers exhibit reduced levels of dryness and discomfort after 12 weeks of Xiidra use compared to baseline.

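### Does the primary analysis need a written rule for the case where only one of discomfort and dryness clears the 10-unit margin?

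*Combined protocol and SAP*

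**What the plan says.** Section 10.1 commits to "Superiority testing for the primary outcome variable (i.e. VAS ratings for CL-related discomfort and dryness" at 12 weeks against baseline), "using a superiority margin of 10 units on the 100-point scale". The level is given once: "Statistical significance will be set at 5" per cent, with no mention of sides. Table 4 lists repeated-measures ANOVA/MANOVA, Tukey comparisons and the paired t-test for the VAS ratings, and ties none of them to the margin.

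The other relevant places are:

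- Section 2 uses the plural: "The primary outcome variables for this study are subjective ratings of" discomfort and dryness, on the same scale and at the same time point.
- Section 3 gives the hypothesis: "symptomatic CL wearers exhibit reduced levels of dryness and discomfort after 12 weeks of Xiidra use compared to baseline". It has no margin and no success rule.
- Section 4.2.1 calls the study a pilot and judges 40 wearers "sufficiently large to detect differences in comfort ratings at 12 weeks compared to baseline". Dryness and the margin are not mentioned there.
- Section 4.5.2 describes the instrument: "the VAS includes the following items: burning/stinging; itching; foreign body sensation; eye discomfort; eye dryness; photophobia; pain". The list contains no combined discomfort-and-dryness item. Appendix 2, which holds the scale itself, is not in the text available.
- Section 4.4.2 takes the VAS before the first drop at Visit 2. Later in the same visit it lists "Post-drop: Subjective ratings of symptoms and tolerability".

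**The concern.** A margin, a significance level and a primary hypothesis together look like a confirmatory test, and such a test should give one verdict for any data. Here it might not. If discomfort clears 10 units and dryness does not, an 'either' rule gives success and a 'both' rule gives failure on the same data. Averaging the two items is a third possibility. The study is open-label and the analysis unmasked, so a rule not fixed beforehand could be chosen once the results are known.

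The wording seems to add to the doubt. Section 2 speaks of outcome variables, section 10.1 of a single variable, and section 4.2.1 of comfort alone. Unstated sidedness also moves the bar that the observed mean must pass. At stake would be the meaning of a claim that the primary objective was met, and the chance of making that claim falsely.

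**Working it through.** **Do the sections conflict?** Sections 2 and 10.1 name the same ratings, scale and comparison; they differ only in plural against singular, and section 10.1 explains its singular with the plural 'ratings'. Section 4.2.1 gives the reason for the number 40 and does not define the primary outcome. Sections 2, 3 and 10.1 all join the two symptoms with 'and'; none says 'or' or 'average'. So there is one definition, loosely worded, with no explicit success rule.

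**Inputs.** From the documents: 40 completers (sections 4.2.1 and 4.2.2), a 10-unit margin and a 5% level (section 10.1), and paired comparison with baseline. The 40 cannot be reproduced, because no effect, SD or power is given. Assumed: correlation between the two changes r = 0.3, 0.5, 0.7, 0.9; equal power per item of 80% or 50%; SD of change 15 to 30 where an SD is needed.

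**How likely is a split result?** The test is a paired t-test against 10 with 39 degrees of freedom. The critical value is 2.0227 (two-sided 5%) or 1.6849 (one-sided 5%). For 80% power, the excess over the margin must be 0.454 SD (two-sided) or 0.400 SD (one-sided). With per-item power p, P(either) = 2p − P(both) and P(split) = 2p − 2·P(both). Simulation (200,000 trials per setting, two-sided 5%) gives, at p = 0.80:

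| r | both | either | split |
|---|---|---|---|
| 0.3 | 66.5% | 93.5% | 27.0% |
| 0.5 | 68.6% | 91.4% | 22.9% |
| 0.7 | 71.3% | 88.9% | 17.6% |
| 0.9 | 74.8% | 85.1% | 10.3% |

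Check at r = 0.3: 160 − 66.5 = 93.5 and 160 − 2 × 66.5 = 27.0. One-sided runs differ by at most 0.3 points. At 50% power per item the split rate is about 41, 34, 26 and 15%.

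**The most extreme contrast.** With one item at 80% power and the other exactly at the margin, success is about 80% under 'either', 2.5% (two-sided) or 5% (one-sided) under 'both', and 30 to 41% if the items are averaged (two-sided).

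**False success with both items exactly at the margin.** Let a be the error in the improving direction. Then P(either) = 2a − P(both), with P(both) from the bivariate normal.

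| r | a = 5%: both | a = 5%: either | a = 2.5%: both | a = 2.5%: either |
|---|---|---|---|---|
| 0.3 | 0.71% | 9.29% | 0.24% | 4.76% |
| 0.5 | 1.22% | 8.78% | 0.46% | 4.54% |
| 0.7 | 1.96% | 8.04% | 0.83% | 4.17% |
| 0.9 | 3.19% | 6.81% | 1.48% | 3.52% |

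The t-based simulation at a = 2.5% gives 3.6 to 4.9% for 'either', the same within simulation error. Under 'both', false success cannot exceed a, whatever the true state of the second item.

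**Sidedness.** The observed mean improvement needed is 10 + t × SD/√40. For SD 15, 20, 25, 30 it is 14.0, 15.3, 16.7, 18.0 one-sided and 14.8, 16.4, 18.0, 19.6 two-sided. The choice moves the bar by 0.8 to 1.6 units on a 100-point scale.

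**Which rating is baseline?** Section 4.4.2 fixes the order of procedures, places baseline measurements before the drops are dispensed, and labels the later rating separately as post-drop. Baseline is therefore the earlier rating.

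**The case for a change.** The strongest case for a change is that this pilot chose to specify a superiority margin and a level, and a test without a decision rule has no defined verdict. Section 3 says 'and', but against baseline and with no margin, so it does not strictly supply the rule for section 10.1. A split is not a rare corner case, the figures reproduce, and a remedy would cost a few sentences.

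Much of this stands. The success rule and the sidedness are indeed missing, and writing them down beforehand would be good practice. What does not carry over is the harm. The 'either' and 'average' readings, which drive the large contrasts, have no support in the text. At two-sided 5% even an unadjusted 'either' rule stays below 5%, though above the 2.5% upper tail. The 80% against 2.5% contrast also needs one item to sit exactly on the margin while the other is well powered. That an analyst might pick the rule after seeing the data is possible, but a report giving both items against 10 units shows any reader which one passed.

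**Conclusion.** The concern does not call for a change. What is missing is a detail that an analyst can fill sensibly: test eye discomfort and eye dryness each against 10 units with the paired t-test already in Table 4, report both, and read the objective as the hypothesis words it, with both symptoms reduced. That reading needs no adjustment of the level. Its price is joint power of about 67 to 75% when each item has 80%, at assumed correlations of 0.3 to 0.9.

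A split result, in roughly 10 to 27% of trials under those assumptions, would leave the summary word 'met' open to argument. The two estimates and their tests would still be sound. In a single-arm, open-label pilot whose stated further use is sizing later studies, no decision in the documents depends on a joint verdict. Error above 5% needs two unstated choices together, an 'either' rule and one-sided testing. The conclusion would differ for a confirmatory trial. The power, correlation and SD values are assumptions, since the documents give none.
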